	
 Proportion of patients achieving EASI90 Proportion of patients achieving EASI50 	Descriptive statistics (Observed and NRI)			ITT	Weeks 0 to 16
					ITT Week 24 EE set	Week 24
	Body Surface Area (BSA) Affected by AD	
 BSA score Change from baseline in BSA score 			Descriptive statistics (Observed)	ITT
			SCORing Atopic Dermatitis (SCORAD)	
 SCORAD score Change from baseline in SCORAD score Percent change from baseline in SCORAD score 		Descriptive statistics (Observed)

 Proportion of patients achieving SCORAD75 Proportion of patients achieving SCORAD90 	Descriptive statistics (Observed and NRI)	ITT			Weeks 0 to 16	
				ITT Week 24 EE set	Week 24	Exploratory analysis

Abbreviations: AD = atopic dermatitis; EE = efficacy evaluable; ITT = intent-to-treat; MMRM = mixed-model repeated measures; NRI = nonresponder imputation.

APP.1.2.12.1. Primary Outcome and Methodology

The validated IGA for AD uses the clinical characteristics of erythema, papulation/induration, oozing/crusting and lichenification to produce a single-item score ranging from 0 to 4. The primary analysis of the study is to estimate the effect of starting baricitinib 2-mg on clinical measures and patient-reported outcomes as assessed by the proportion of patients with a response of IGA 0, 1, or 2 assessed at Week 16 using the ITT population assuming that treatment response disappears after the patient is rescued or discontinued study or study treatment. This will serve as the primary estimand. In this estimand, missing data due to the application of the censoring rule and the occurrence of other noncensor intercurrent events will be imputed using the NRI method described in Section [6.4.1](#).

APP.1.2.12.2. Secondary and Exploratory Efficacy Analyses

There will be no adjustment for multiple comparisons for any analyses. The secondary and exploratory efficacy analyses are detailed in Section [6.2.3](#) and [Table JAHN.6.4](#). Health outcomes analyses are described in Section [APP.1.2.13](#).

Note that the exploratory efficacy analyses on a continuous outcome that is measured over time uses a slightly different estimand which is to estimate the effect of starting baricitinib 2-mg on a specific endpoint evaluated at specified time points using the ITT population assuming all patients remained in their treatment throughout the defined period of the study.

APP.1.2.13. Health Outcomes/Quality-of-Life Analyses

The general methods used to summarize health outcomes and quality-of-life measures, including the definition of baseline value for assessments are described in Section [APP.1.2.3.2.2](#).

Health outcomes and quality-of-life measures will generally be analyzed according to the formats discussed in Section [APP.1.2.12](#).

[Table JAHN.6.6](#) includes the descriptions and derivations of the health outcomes and quality-of-life measures. [Table APP.1.4](#) provides the detailed analyses including analysis type, method and imputation, population, and time point for health outcomes and quality-of-life measures.

Table APP.1.4. Description of Health Outcomes and Quality-of-Life Measures Analyses

Measure	Variable	Analysis Method (Section 6.2.3)	Population (Section 6.2.1)	Time Point	Analysis Type
Itch Numeric Rating Scale (NRS)	
 ▪ Itch NRS score ▪ Change from baseline in Itch NRS score ▪ Percent change from baseline Itch score 	Descriptive statistics	ITT	Weeks 0 to 16	Exploratory analysis
	
 ▪ Proportion of patients with a 4-point improvement from baseline of originating study in Itch NRS in subgroup of patients who had baseline Itch NRS ≥ 4 	Descriptive statistics (Observed and NRI)	ITT	Weeks 0 to 16	Secondary analysis
Skin Pain Numeric Rating Scale (NRS)	
 ▪ Skin Pain NRS score ▪ Change from baseline in Skin Pain NRS score 	Descriptive statistics (Observed)	ITT	Weeks 0 to 16	Exploratory analysis
	
 ▪ Proportion of patients with a 4-point improvement from baseline of originating study in Skin Pain NRS in subgroup of patients who had baseline Skin Pain NRS ≥ 4 	Descriptive statistics (Observed and NRI)	ITT	Weeks 0 to 16	Exploratory analysis
Atopic Dermatitis Sleep Scale (ADSS)	
 ▪ ADSS item scores ▪ Change from baseline in ADSS item scores 	Descriptive statistics (Observed)	ITT	Weeks 0 to 16	Exploratory analysis
	
 ▪ Proportion of patients with a 1.5 point improvement from baseline of originating study in ADSS2 score in subgroup of patients who had baseline ADSS2 score ≥ 1.5 ▪ Proportion of patients with a 2 point improvement from baseline of originating study in ADSS2 score in subgroup of patients who had baseline ADSS2 score ≥ 2 	Descriptive statistics (Observed and NRI)	ITT	Weeks 0 to 16	Exploratory analysis

Measure	Variable	Analysis Method (Section 6.2.3)	Population (Section 6.2.1)	Time Point	Analysis Type
Patient Global Impression of Severity–Atopic Dermatitis (PGI-S-AD)	
 ▪ PGI-S-AD score ▪ Change from baseline in PGI-S-AD score 	Descriptive statistics (Observed)	ITT	Weeks 0 to 16	Exploratory analysis
Patient-Oriented Eczema Measure (POEM)	
 ▪ POEM score ▪ Change from baseline in POEM score 	Descriptive statistics (Observed)	ITT	Weeks 0 to 24	Exploratory analysis
	
 ▪ Proportion of patients with a 4 point improvement from baseline of originating study in POEM score in subgroup of patients who had baseline POEM score ≥ 4 	Descriptive statistics (Observed and NRI)	ITT	Weeks 0 to 16	Exploratory analysis
			ITT Week 24 EE set	Week 24	Exploratory analysis
Hospital Anxiety Depression Scale (HADS)	
 ▪ HADS domain scores and total scores ▪ Change from baseline in HADS domain and total scores 	Descriptive statistics (Observed)	ITT	Weeks 0 to 24	Exploratory analysis
Dermatology Life Quality Index (DLQI)	
 ▪ DLQI total score ▪ Change from baseline in DLQI ▪ Observed and change from baseline in domain scores 
 - Symptoms and feelings - Daily activities - Leisure - Work and school - Personal relationships - Treatment 	Descriptive statistics (Observed)	ITT	Weeks 0 to 24	Exploratory analysis
			ITT	Weeks 0 to 16	Exploratory analysis
	
 ▪ Proportion of patients with a DLQI (0, 1) response ▪ Proportion of patients with a 4 point improvement from baseline of originating study in DLQI in subgroup of patients who had baseline DLQI ≥ 4 	Descriptive statistics (Observed and NRI)	ITT Week 24 EE set	Weeks 24	Exploratory analysis

Measure	Variable	Analysis Method (Section 6.2.3)	Population (Section 6.2.1)	Time Point	Analysis Type
Work Productivity and Activity Impairment: Atopic Dermatitis (WPAI-AD)	Observed and Change from baseline in employment status	Descriptive statistics (observed)	ITT	Weeks 0 to 24	Exploratory analysis
	Observed and Change from baseline in: 
 ▪ absenteeism ▪ presenteeism ▪ overall work impairment ▪ impairment in activities 	Descriptive statistics (Observed)	ITT	Weeks 0 to 24	Exploratory analysis
European Quality of Life–5 Dimensions–5 Levels (EQ-5D-5L)	Observed values in 
 ▪ EQ-5D mobility ▪ EQ-5D self-care ▪ EQ-5D usual activities ▪ EQ-5D pain/ discomfort ▪ EQ-5D anxiety/ depression 	Descriptive statistics (Observed)	ITT	Weeks 0 to 24	Exploratory analysis
	Observed and Change from baseline in 
 ▪ EQ-5D VAS ▪ EQ-5D-5L UK Population-based index score ▪ EQ-5D-5L US Population-based index score 	Descriptive statistics (Observed)	ITT	Weeks 0 to 24	Exploratory analysis

Abbreviations: AD = atopic dermatitis; EE = efficacy evaluable; ITT = intent-to-treat; NRI = nonresponder imputation.

APP.1.2.14. Bioanalytical and Pharmacokinetic / Pharmacodynamic Methods

Pharmacokinetic, pharmacodynamic, and biomarker analyses will not be conducted.

APP.1.2.15. Safety Analyses

The safety data from this addendum will be pooled with the bari 2-mg treatment group from Study JAHN and will follow the same planned analyses given in Section 6.14. Refer to Section 6.14 for the planned analyses.

APP.1.2.15.1. Extent of Exposure

Refer to Section 6.14.1 for the planned analyses.

APP.1.2.15.2. Adverse Events

Refer to Section 6.14.2 for the planned analyses.

APP.1.2.15.2.1. Common Adverse Events

Not applicable.

APP.1.2.15.2.2. Serious Adverse Event Analyses

Refer to Section 6.14.2.2 for the planned analyses.

APP.1.2.15.2.3. Other Significant Adverse Events

Refer to Section 6.14.2.3 for the planned analyses.

APP.1.2.15.3. Clinical Laboratory Evaluation

Refer to Section 6.14.3 for the planned analyses.

APP.1.2.15.4. Vital Signs and Other Physical Findings

Refer to Section 6.14.3 for the planned analyses.

APP.1.2.15.5. Special Safety Topics, including Adverse Events of Special Interest

Refer to Section 6.14.5 for the planned analyses.

APP.1.2.16. Subgroup Analyses

Subgroup analyses will not be performed for Study JAHN(7.1).

APP.1.2.17. Protocol Deviations

Protocol deviations will be analyzed as described in Section 6.16 using the ITT population.

APP.1.2.18. Interim Analyses and Data Monitoring

Refer to Section 6.17 for the planned analyses.

APP.1.2.19. Planned Exploratory Analyses

The planned exploratory analyses are described in Section 6.18.

APP.1.2.20. Annual Report Analyses

Refer to Section 6.19.

APP.1.2.21. Clinical Trial Registry Analyses

Refer to Section 6.20.

APP.1.3. Unblinding Plan

Refer to Section 7.

APP.1.4. References

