### **Other Exclusions**

- [30] are unable or unwilling to make themselves available for the duration of the study and/or are unwilling to follow study restrictions/procedures.
- [31] are currently enrolled in any other clinical trial involving an investigational product or any other type of medical research judged not to be scientifically or medically compatible with this study.
- [32] have participated within the last 30 days in a clinical study involving an investigational product. If the previous investigational product has a long half-life (2 weeks or longer), at least 3 months or 5 half-lives (whichever is longer) should have passed.

- [33] have previously been enrolled in this study or any other study investigating baricitinib or who have experienced hypersensitivity to the active substance or to any of the excipients.
- [34] are investigator site personnel directly affiliated with this study and/or their immediate families. Immediate family is defined as a spouse, parent, child, or sibling, whether biological or legally adopted.
- [35] are Lilly or Incyte employees or their designee.

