##### *Treatment Period 2: Weeks 52-104*

As patients from JAHN(7) will have been treated with open-label baricitinib for 52 weeks, similar to patients enrolled in the main protocol who were on placebo at the time of entry, and since patients are randomized at the start of treatment period 2, data from patients in JAHN(7) who participate in the substudy during treatment period 2 may be combined with the corresponding population from the main protocol and will be analyzed as described in Section 10 of the main protocol.

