For the DBL in December 2021 and final DBL, the following analysis populations are defined for efficacy and health outcome analyses.

Randomized Downtitration Withdrawal Substudy Population: All patients (including open-label patients) who are rerandomized at Week 52, enter the substudy, and receive at least 1 dose of the IP in Period 2.

Re-Treatment Substudy Population: A subset of Randomized Downtitration Withdrawal Substudy Population who experience IGA ≥ 3 at any time in Period 2 and receive at least 1 dose of retreatment of the original dose.

Period 2 Nonsubstudy Population: All patients randomized at Week 0 of main Study JAHN (excluding open-label patients) who are not eligible to enter the substudy at Week 52 and receive at least 1 dose of the IP in Period 2.

Open-Label Period 2 Nonsubstudy Population: All patients enrolled in the open-label addendum who are not eligible to enter the substudy at Week 52 and receive at least 1 dose of the IP in Period 2.

Long-Term Baricitinib 4 mg Population: Patients initially randomized to baricitinib 4 mg in the originating studies and remain on 4-mg up to Week 52 of Study JAHN. At Week 52 of Study JAHN, patients also need to continue 4-mg and receive at least one dose in Period 2 regardless of eligibility of entering sub-study.

Safety population: For the purpose of Study JAHN alone, the safety population is defined as all patients who received at least 1 dose of IP in Study JAHN and who did not discontinue from the study for the reason ‘Lost to Follow-up’ at the first postbaseline visit in Study JAHN. For the safety analysis of Treatment Period 2, patients with at least 1 dose of IP in Treatment Period 2 will be included in the safety analysis of Treatment Period 2.

Safety analyses will be performed using the safety population and will be analyzed according to the following treatment groups (or cohorts) defined in [Table JAHN.6.1](#). Patients will be analyzed according to the dosing regimen to which they were assigned.

Table JAHN.6.1. Safety Population Treatment Groups

Treatment Groups for Treatment Period 1 (Week 0-52)	Definition
PBO	Placebo at entry to Study JAHN followed to end of Treatment Period 1 or censored at treatment change
BARI 1 mg	BARI 1 mg followed to end of Treatment Period 1 or censored at dose or treatment change
PBO/BARI 1 mg to BARI 2 mg	PBO/BARI 1 mg switching to BARI 2 mg at entry to Study JAHN followed to end of Treatment Period 1 or censored at dose or treatment change

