BARI 2 mg	BARI 2 mg followed to end of Treatment Period 1 or censored at dose or treatment change
PBO/BARI 1 mg/BARI 2 mg to BARI 4 mg	PBO/BARI 1 mg/BARI 2 mg switching to BARI 4 mg at entry to Study JAHN followed to end of Treatment Period 1 or censored at dose or treatment change
BARI 4 mg	BARI 4 mg followed to end of Treatment Period 1 or censored at dose or treatment change
Pooled BARI	BARI 1 mg/BARI 2 mg/BARI 4 mg at entry to Study JAHN followed to end of Treatment Period 1 or censored at dose or treatment change
Treatment Groups for Treatment Period 2 (Week 52-200)	Definition
BARI 2 mg to PBO	Randomized to PBO in Treatment Period 2 (previously treated with BARI 2 mg) followed to end of study or censored at retreatment with BARI 2 mg

Treatment Groups for Treatment Period 2 (Week 52-200)	Definition
BARI 2 mg to BARI 1 mg	Randomized to BARI 1 mg in Treatment Period 2 (previously treated with BARI 2 mg) followed to end of study or censored at retreatment with BARI 2 mg
BARI 2 mg to BARI 2 mg	Randomized to stay on BARI 2 mg in Treatment Period 2 followed to end of study
BARI 4 mg to PBO	Randomized to PBO in Treatment Period 2 (previously treated with BARI 4 mg) followed to end of study or censored at retreatment with BARI 4 mg
BARI 4 mg to BARI 2 mg	Randomized to BARI 2 mg in Treatment Period 2 (previously treated with BARI 4 mg) followed to end of study or censored at retreatment with BARI 4 mg
BARI 4 mg to BARI 4 mg	Randomized to stay on BARI 4 mg in Treatment Period 2 followed to end of study
BARI 2 mg	Not part of the substudy, stayed on BARI 2 mg in Treatment Period 2 followed to end of study (this treatment group includes the open-label BARI 2 mg addendum patients)
BARI 4 mg	Not part of substudy, stayed on BARI 4 mg in Treatment Period 2 followed to end of study
Treatment Group for Treatment Periods 1 and 2 (Week 0-104) (for Box Plots Only)	Definition
PBO	Placebo at entry to Study JAHN followed to end of study or censored at treatment change
BARI 1 mg	BARI 1 mg followed to end of study or censored at dose or treatment change
BARI 2 mg to PBO	BARI 2 mg in Treatment Period 1, rerandomized to PBO in Treatment Period 2 followed to end of study or censored at retreatment with BARI 2 mg
BARI 2 mg to BARI 1 mg	BARI 2-mg in Treatment Period 1, rerandomized to BARI 1 mg in Treatment Period 2 followed to end of study or censored at retreatment with BARI 2 mg

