6.11. Efficacy Analyses

The general methods used to summarize efficacy data, including the definition of baseline value for assessments are described in Section 6.2.

Efficacy analyses will generally be analyzed according to the groups in Table JAHN.6.3 and patients will be analyzed according to the IP being analyzed in the objective.

Table JAHN.6.3. Efficacy Analyses: Comparisons or Treatment Paradigms

Treatment Period	Treatment Groups: Originating Study Treatment to JAHN Treatment	Comparison or Treatment Paradigms	Analysis
Treatment Period 1 (main JAHN protocol)	Responders and Partial Responders: PBO to PBO (PBO), BARI 1 mg to BARI 1 mg (BARI 1 mg), BARI 2 mg to BARI 2 mg (BARI 2 mg), BARI 4 mg to BARI 4 mg (BARI 4 mg)	PBO, BARI 1 mg, BARI 2 mg, BARI 4 mg; descriptive	Primary, Secondary, Exploratory
	Nonresponders: PBO to BARI 2 mg, PBO to BARI 4 mg, BARI 1 mg to BARI 2 mg, BARI 1 mg to BARI 4 mg, BARI 2 mg to BARI 2 mg, BARI 2 mg to BARI 4 mg, BARI 4 mg to BARI 4 mg	PBO to BARI 4 mg vs PBO to BARI 2 mg; BARI 1 mg to BARI 4 mg vs BARI 1 mg to BARI 2 mg; BARI 2 mg to BARI 4 mg vs BARI 2 mg to BARI 2 mg	Secondary, Exploratory
Treatment Period 2 (Randomized Withdrawal and Downtitration SubStudy)	Treatment Groups: Bari 4 mg at Week 52 Bari 4 mg to Bari 2 mg Bari 4 mg to PBO Bari 2 mg at Week 52	Bari 4 mg to Bari 2 mg Bari 4 mg to PBO	Secondary

Treatment Period	Treatment Groups: Originating Study Treatment to JAHN Treatment	Comparison or Treatment Paradigms	Analysis
	Bari 2 mg to Bari 1 mg Bari 2 mg to PBO	Bari 2 mg to Bari 1 mg Bari 2 mg to PBO	
Treatment Period 2 (Non substudy) (main JAHN population)	Treatment Groups: Bari 4 mg Bari 2 mg Bari 1 mg PBO	No comparison	Secondary, Exploratory
Treatment Period 2 (Non substudy) (open label Bari 2mg population)	Treatment Groups: Bari 2mg	No comparison	Secondary, Exploratory

Abbreviations: BARI = baricitinib; PBO = placebo.

[Table JAHN.6.4](#) includes the descriptions and derivations of the primary, secondary, and exploratory efficacy outcomes.

[Table JAHN.6.5](#) provides the detailed analyses including analysis type, method and imputation, population, time point, and comparisons for efficacy analyses.

Table JAHN.6.4. Description and Derivation of Primary, Secondary, and Exploratory Efficacy Outcomes

Measure	Description	Variable	Derivation / Comment	Imputation Approach if Missing Components

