Intent-to-treat (ITT) population: The ITT population analysis set is defined as all enrolled patients in Study JAHN(7.1).

Unless otherwise specified, the efficacy and health outcome analyses will be conducted on the ITT population (Gillings and Koch 1991).

Safety population: The Safety population for this addendum is defined the same as the safety population in Section 6.2.1.

Safety analyses for this addendum will be performed on the safety population and data will be pooled with the data from Study JAHN.

For the database lock that supports the US submission, the population for this addendum, Week 24 efficacy and health outcome analyses will be conducted on the **Week 24 efficacy evaluable set**. This subset of the ITT Population is anchored on the database cut-off date for the US DBL (13 December 2019). Specifically, a patient will be included in the Week 24 Efficacy Evaluable set if their Week 24 visit has occurred or their expected Week 24 visit date plus a 15-day buffer is on or prior to the database cutoff date. The expected Week 24 visit date will be calculated as follows: Date of first dose date + (24 weeks * 7 days) + 15 days.

APP.1.2.3.2.2. Definition of Baseline and Postbaseline Measures

The baseline value for the efficacy and health outcome analyses is defined similarly to Section 6.2.2 except it uses the date of first study drug administration (expected at Week 0, Visit 1) in place of the first study drug administration in the originating study. The baseline value for the daily diary assessments (Itch Numeric Rating Scale (NRS), Atopic Dermatitis Sleep Scale, Skin Pain NRS, Patient Global Impression of Severity-AD) is also defined similarly (using the date of first study administration in Study JAHN).

For the purpose of Study JAHN addendum, the safety analyses will be conducted as described in Section 6.2.2.

Postbaseline measurements are described in Section 6.2.2.

APP.1.2.3.2.3. Analysis Methods

All discrete efficacy and health outcome variables will be summarized using frequencies and percentages. The 95% confidence intervals will also be provided.

APP.1.2.3.2.4. Derived Data

Refer to Section 6.2.4, using the Study JAHN(7.1) baseline where applicable.

APP.1.2.4. Adjustments for Covariates

Not applicable.

APP.1.2.5. Handling of Dropouts or Missing Data

Refer to Section 6.4.

The censoring rule will be applied to all efficacy and health outcome endpoints conducted for the ITT population.

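### In Period 1 safety tables, open-label addendum patients new to baricitinib share a column with patients already about 16 weeks into 2 mg, so the column mixes pre-drug and on-drug baselines

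*SAP*

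**What the plan says.** SAP APP.1.2.15 gives the rule: "The safety data from this addendum will be pooled with the bari 2-mg treatment group from Study JAHN". APP.1.2.3.2.1 says more loosely that the addendum's "data will be pooled with the data from Study JAHN". No addendum-only AE, laboratory or vital-sign display is planned. Protocol Section 4.8.2 is permissive: it allows the addendum's safety population to be combined with the corresponding main-protocol population but does not require it.

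The Period 1 panel of Table JAHN.6.1 (SAP Section 6.2.1) has two rows for feeder-study patients on 2 mg. One is for switchers: "PBO/BARI 1 mg switching to BARI 2 mg at entry to Study JAHN followed to end of Treatment Period 1". The other reads "BARI 2 mg followed to end of Treatment Period 1 or censored at dose or treatment change" and does not mention addendum patients. The Period 2 non-substudy row and the combined box-plot row for BARI 2 mg both say that they include addendum patients.

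Protocol exclusion criterion 33 keeps out patients who "have previously been enrolled in this study or any other study investigating baricitinib". SAP Section 5.1 says that feeder patients arrive with about 16 weeks of study treatment. Sections 6.2.2 and 6.14.2 set the safety baseline and the start of treatment emergence at the first dose in Study JAHN, for all patients alike.

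**The concern.** The two sets of patients in the Period 1 BARI 2 mg column are at different points in their exposure when the clock starts. An adverse event, or a laboratory shift, that appears in the first 16 weeks on 2 mg counts as new in an addendum patient. In a continuer the same event or shift has already happened and sits in the baseline. The addendum group also knows its treatment; the continuers are blinded.

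These displays are not all purely descriptive. Section 6.14.3 attaches ANCOVA p-values to the box plots and Fisher's exact tests to the treatment-emergent high and low counts. Section 6.14.4 applies the same analyses to vital signs. The addendum was added to enlarge the safety database for this dose (Protocol Section 3), and under the planned grouping a reader cannot see the safety profile of patients starting 2 mg in it.

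**Working it through.** **The plan's own figure.** The only derived addendum figure is the expected substudy entry: 250 × 0.80 × 0.30 = 60, which matches the stated 60 (Protocol Sections 4.4 and 4.8.1). No figure is given for the safety pooling, so the main check is a comparison of definitions.

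**Step 1: who is in the Period 1 BARI 2 mg row.** Feeder patients on placebo or 1 mg who move to 2 mg have their own row. The feeder patients left on 2 mg are those who were on it before. Table JAHN.6.3 uses the label in the same way for responders and partial responders, listing the arm as "BARI 2 mg to BARI 2 mg (BARI 2 mg", where the bracket gives the short name. That the row means continuers is a sound inference, but the SAP does not state it.

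**Step 2: what the common time origin means for each group.**

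| | Addendum patient | 2-mg continuer, no washout |
|---|---|---|
| Earlier baricitinib in a trial | none (criterion 33) | about 16 weeks of 2 mg (SAP 5.1) |
| Blinding in Period 1 | open label (Protocol 4.6.5) | double-blind |
| Safety baseline (SAP 6.2.2) | before any dose | last originating-study visit, on drug |
| Weeks since first 2-mg dose covered by Period 1 | 1 to 52 | about 17 to 68 (16 + 52 = 68) |

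**Step 3: consequences by display.**

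- TEAEs (Section 6.14.2). An event that begins in exposure weeks 1 to 16 and persists without worsening is treatment-emergent in an addendum patient. In a continuer it began before the first JAHN dose and is not.
- Treatment-emergent high or low (Section 6.14.3). A patient counts only if within the limit at all baseline visits. A continuer whose value crossed the limit on drug in the feeder study, and was still beyond it at the last feeder visit, cannot count. An addendum patient with the same course does.
- Change from baseline. Let f(t) be the mean change from the pre-drug value at t weeks of exposure, taken as the same in both groups. At JAHN week w the addendum patients show f(w). Continuers without washout show f(16 + w) − f(16). With addendum share s, the column shows s·f(w) + (1 − s)·[f(16 + w) − f(16)].

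**Step 4: illustration of size.** The number of continuers (c) is not in the documents, so 50 to 400 is assumed. Share s = 250/(250 + c). The event risks are also assumed: 20% in new starters, and 10% or 15% in continuers. Pooled risk = s × 20% + (1 − s) × the continuer risk.

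| Continuers c | Share s | Pooled, 20% v 10% | Pooled, 20% v 15% |
|---|---|---|---|
| 50 | 83.3% | 18.3% | 19.2% |
| 100 | 71.4% | 17.1% | 18.6% |
| 150 | 62.5% | 16.3% | 18.1% |
| 200 | 55.6% | 15.6% | 17.8% |
| 300 | 45.5% | 14.5% | 17.3% |
| 400 | 38.5% | 13.8% | 16.9% |

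For a laboratory value, suppose that the whole drug effect D is reached by week 16 and then stays level. From JAHN week 16 on, addendum patients show D and continuers show 0. The column then shows s × D, from 0.83 D down to 0.38 D over the same range of c.

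**The case against.** The pooling is prespecified, the protocol permits it, and SAP Version 3 already clarified it. It also serves the addendum's purpose of adding exposure at 2 mg. Section 6.14 places the fuller safety assessment in integrated analyses that are not available here. SAEs are listed individually, and addendum disposition is reported separately (APP.1.2.8). A weighted average always lies between its parts, and with equal risks in the two groups it misleads nobody. All of this stands, and it limits the weight of the point. None of it lets a reader of the JAHN tables separate the two baselines.

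Four stronger readings are tempting, and the documents do not support them.

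- A reader might infer that the switcher row exists to isolate first exposure. The SAP gives no reason for the row. It includes patients who had 1 mg, and the matching 4-mg row includes patients who had 1 mg or 2 mg, so the rows separate a change of dose.
- The protocol calls addendum patients "similar to patients enrolled in the main protocol who were on placebo at the time of entry". That sentence stands under Treatment Period 2. It supports combining substudy data after 52 weeks of treatment and does not address Period 1 safety groups.
- A reader might see a confounded comparison of 2 mg with 4 mg. No such safety contrast is named. Section 6.2.3 tests categorical safety data against placebo, and continuous data against placebo or an appropriate comparator.
- A reader might think that switchers to 2 mg are kept apart throughout. Only the Period 1 panel does so. The Period 2 non-substudy and box-plot rows are set by JAHN dose. The February 2021 Period 1 AE tables have five groups (placebo, 1, 2 and 4 mg, pooled baricitinib) and no switcher row.

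**Conclusion.** The point holds for Treatment Period 1. Read with the Period 1 panel of Table JAHN.6.1, APP.1.2.15 puts patients starting 2 mg and patients about 16 weeks into 2 mg in one column under one time origin. Their TEAE, treatment-emergent laboratory and vital-sign, and change-from-baseline results are not the same quantity.

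This rests on two readings: that the BARI 2 mg row means continuers (by elimination), and that continuers without washout were still taking 2 mg at their last feeder visit. The shares and pooled rates are illustrations on assumed counts and risks, not estimates; the size could be zero if nothing changes in the first 16 weeks on drug.

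The point does not carry over in the same form to Period 2. There the SAP plans AE analyses only (Section 6.2.2), and both groups have completed Period 1 on treatment. It is a worthwhile, inexpensive improvement to reporting and does not threaten the trial's efficacy conclusions.

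**What to change.** 1. In the Period 1 panel of Table JAHN.6.1, state which row holds the addendum patients, as the later panels already do.
2. In the Period 1 exposure, AE, laboratory and vital-sign displays, show the open-label addendum as its own column. Keep the pooled 2-mg column as an additional total.
3. In Section 6.2.1, state where the placebo or 1 mg to 2 mg patients fall in the five-group AE tables for the February 2021 lock.

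No added laboratory column is needed for Period 2.

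The cost is a wider table and some re-display of data that are already locked; SAP Version 8 records that data to Week 104 are locked. Section 6.14 limits the February 2021 and final-lock safety output to disposition and AE tables. The laboratory and vital-sign columns would therefore be supplementary to those two locks. No new data and no new model are required.
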